Placebo: Normal Saline will be administered following exactly the same procedure as that for IV iron.

Agent and administration for oral iron and placebo

Oral iron: This study will use Ferrous sulfate 325 mg tablets. The medication is to be taken together twice a day. If significant stomach distress occurs the patient may elect to take the medication with food and must then notify the research coordinator. The pills will be provided in opaque bottles with exactly enough for 7 weeks and a pill count will be made at the 6-week follow up to determine compliance. The oral pills will be stopped at the 6-week evaluation time.

Placebo: Standard vitamin C 250mg, given in the same bottle as the oral iron.

Subject schedule: (See appendix for chart of visits)

There will be 2 – 3 visits at the [name] clinic and telephone evaluations conducted by the Hopkins doctors prior to the start of treatment. After the first IV treatment there will be a telephone evaluation at 1, 2 and 4 weeks later and a clinic visit for blood tests at 4 weeks after the first of the pairs of IV treatment and again at about 6 weeks after the first of the pair of IV iron treatments. At 6 weeks after treatment responders will continue in the study with telephone evaluations of their RLS symptoms and medications at about 3, 6, 9 and 12 months after the first IV treatment. At 6 weeks after treatment non-responders will be given the option of receiving the IV ferumoxytol following the same procedure as at the initial treatment with a 6-week period of observation except this will be open label. Both the patient and the coordinator will know that ferumoxytol was given at this repeat dosing. This option will be given only if the patient continues to meet all the inclusion/exclusion criteria for the study noted below, except they will not be excluded for their prior IV treatment in this study. Those receiving the repeat IV dosing at 6 weeks will follow all the same procedures used after the first IV dosing, e.g. telephone safety checks and RLS symptom evaluations at 24-48 hours, 1 week and 4 weeks after initial treatment and a repeat clinic visit at about 6 weeks after the first of the two repeated IV treatment. This 6-week clinic visit will repeat blood tests, adverse event reporting and clinical evaluation of the RLS. The responders to this repeated IV treatment will be followed for up to one year following the same procedures as responders. The non-responders will end the study at this point.

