Any other medical condition that, in the opinion of Investigator, may cause the subject to be unsuitable for the completion of the study or place the subject at potential risk from being in the study, e.g. a malignancy, uncontrolled hypertension, unstable ischemic heart disease, or uncontrolled diabetes mellitus

Study Endpoints for each subject

The following are endpoints for each patient in the study :

1. At evaluation in the clinic at about 6 weeks after the first IV iron treatment.
2. Termination of participation because of significant adverse effect from the IV infusion in the hour observed after the infusion.
3. Significant adverse event after starting the iron treatment and before the 6 week follow-up evaluation that was judged to require ending the study.
4. Subject decision not to continue in the study after the treatment and before the final evaluation.
5. [name] decision that it would be harmful to the patient to continue in the study.
6. Patient is non-compliant with study requirements and [name] judges this non-compliance is enough to significantly alter evaluation of the treatment. (Note that stopping the

18 July 2014

oral medication because of intolerance to the treatment is not considered non-compliance, but rather an outcome for the study. Patients discontinuing oral medication for adverse effects may qualify for repeat IV treatment.)

Duration of subject participation:

Participation will continue for 6 weeks after treatment for the primary study and for 12 months after treatment for the extension study for those responding to the initial treatments or the open label repeated IV treatment.

Early termination of study:

Subjects may terminate the study at any time or maybe terminated from the study for non-compliance or if continuation in the study is judged by [name] to be harmful to the patient. A telephone evaluation will be scheduled when possible at the time of early termination. The reason for the early termination will be noted.

Blood tests obtained:

Iron panel, hemoglobin and hematocrit will be obtained from morning fasting venous samples at screening prior to treatment and at 4 and 6 weeks after the first treatment. About 15 ml of blood will be obtained for these tests

An additional 24 ml of blood will be collected for lymphocytes the day of the first IV treatment before the treatment and again at 6 weeks after the treatment.

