The iron panel will include serum iron, ferritin, transferrin saturation and total iron binding capacity.

Blood samples will routinely be obtained at [name] office, but in special cases may be arranged through a remote office, e.g. Quest.

RLS clinical evaluations obtained:

The primary clinical evaluations will be the clinician global rating of improvement (CGI-2), patient global rating of RLS severity (PGI-1) and the international RLS severity scale (IRLS). These will be obtained at each clinic visit and at each telephone evaluation, except CGI-2 will only be obtained after the treatment.

The secondary clinical evaluations will be the MOS sleep scale [13], Fatigue severity scale [14], SF36 short form [15] and the Hospital anxiety and depression scale (HADS) [16]. These will be obtained at baseline and then again at the 6 week post IV clinic evaluation.

Concomitant treatment/medication

ESA, anti-histamines, drugs that treat RLS, dopaminergic treatment and iron drugs beside study drugs are not allowed during the study period

Safety and adverse events

Expected possible adverse events (AE)

Across three randomized clinical a total of 605 patients were exposed to two injections of 510 mg of ferumoxytol [17-19]. Most patients received their second ferumoxytol injection 3 to 8 days after the first injection. Adverse reactions related to ferumoxytol and reported by $\geq 1\%$ of ferumoxytol-treated patients in the randomized clinical trials are listed in the table below. Diarrhea (4.0%), constipation (2.1%) and hypertension (1.0%) have also been reported in ferumoxytol-treated patients. In clinical trials, adverse reactions leading to treatment discontinuation and occurring in ≥ 2 ferumoxytol-treated patients included hypotension, infusion

18 July 2014

site swelling, increased serum ferritin level, chest pain, diarrhea, dizziness, ecchymosis, pruritus, chronic renal failure, and urticaria.

Adverse Reactions	Ferumoxytol 2 × 510 mg elemental iron (n=605)
Nausea	3.1%
Dizziness	2.6%
Hypotension	2.5%
Peripheral Edema	2.0%
Headache	1.8%
Edema	1.5%
Vomiting	1.5%
Abdominal Pain	1.3%
Chest Pain	1.3%
Cough	1.3%
Pruritus	1.2%
Pyrexia	1.0%
Back pain	1.0%
Muscle spasm	1.0%
Dyspnea	1.0%
Rash	1.0%

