Our major problem in testing the treatment benefits for IDA-RLS for either oral or IV iron was not knowing the actual effect size of either treatment. We had as an initial estimates the effect sizes from clinical experience with oral and IV iron therapy for IDA-RLS. Thus, we set the sample size to give adequate power to differentiate IV from oral iron assuming these estimates, without knowing if the estimates were accurate. The decision not to do a placebo control is based on the assumption that the treatment effect size can be adequately determined without a placebo. The decision to use a blinded comparator trial was based on the assumption that we would see differences between the treatments.

METHODS

The study was a randomized, comparative, double-blind study to evaluate effect size and time course of treatment response for RLS-IAD over six weeks. Two medications and two placebos were used with equal random assignment to both groups:

1. *FCM group:* Oral vitamin C, 500 mg tablets taken twice a day (placebo pill) and Ferumoxytol intravenous (IV) 1020 mg in two divided doses over 15 minutes 2-7 days apart
2. *FeSO4 group:* Ferrous sulfate 325 mg (oral) tabs morning and evening and IV saline given over 15 minutes 2-7 days apart (placebo infusion)

IV ferumoxytol, 1020 mg was be offered to those not significantly responding (CGI-I scores less than much or very much improved) at 6 weeks after oral iron and still meeting all the requirements for entry to study.

All patients who presented to a single outpatient Hematology clinic for treatment for their iron deficiency anemia (IDA), completed the Cambridge-Hopkins diagnostic questionnaire (CDQ) as part of their routine clinical evaluation, which was not limited to its use in this study. Those identified by the questionnaire as having RLS were checked for meeting the other inclusion criteria. The research coordinator reviewed the responses to the questionnaire, their clinical history and recent blood values to ensure inclusion criteria were met. If all criteria were met, the research coordinator consented the

patient for enrollment in the study. After consenting, a protocol number was assigned and appropriate blood samples obtained. Diagnosis of RLS was then confirmed by Hopkins-Hening Telephone Diagnostic Interview (HTDI) conducted by [name] or [name].

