For oral iron, ferrous sulfate 325 mg tablets containing 65 mg of elemental iron were used. The pills were taken twice daily on an empty stomach. If significant gastrointestinal perturbation occurred the medication could be taken with food. The oral placebo was standard vitamin C 250 mg tablets given in the same bottle as oral iron.

Following the first IV infusion, telephone evaluations were performed at 7, 14 and 28 days. At four weeks after the first of the pair of IV treatment were completed, blood tests were performed to include hemoglobin concentration and iron parameters (serum iron, total iron binding capacity, serum ferritin, percent transferrin saturation). A six weeks after the first of the pair of IV treatment were completed, another clinic visit was scheduled so a CGI form could be completed by involved medical personnel. At 6 weeks, non-responders were given the option of receiving ferumoxytol as an open-label infusion. At the 6-week clinic visit, repeat blood tests (see above), adverse event reporting and clinical evaluation of the RLS was performed.

Inclusion criteria were as follows:

1. Aged \geq 18 years
2. Diagnosis of RLS based on CHDQ and confirmed by HTDI
3. International RLS Study Group Severity Scale (IRLS) score > 15 .
4. Iron deficiency anemia defined as ID either ferritin < 20 mcg/l, TSAT $< 19\%$, anemia Hb < 13 g/dL for both males and females.
5. Willingness to use contraceptive to avoid pregnancy: Women have to be surgically sterile, post menopausal or use one of the following contraceptives during the whole study period and after the study has ended for at least 5 times plasma biological half-life of the investigational medicinal product: intrauterine devices or hormonal contraceptives (contraceptive pills, implants, transdermal patches, hormonal vaginal devices, or injections with prolonged release).
6. Willingness to participate and signing the informed consent form

Exclusion criteria were as follows:

1. Iron overload or disturbances in utilization of iron (e.g. haemochromatosis and hemosiderosis)
2. Decompensated liver cirrhosis or active hepatitis (ALAT > 3 times upper limit of normal)
3. Serum ferritin > 500 ng/mL or transferrin saturation $> 40\%$
4. Active acute or chronic infections (assessed by clinical judgment that may be indicated by white blood cells (WBC) and C-reactive protein (CRP) when these are available)
5. Rheumatoid arthritis with symptoms or signs of active inflammation
6. Pregnant and nursing women

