Subjects could terminate the study at any time for could be terminated from the study for non-compliance or if continuation in the study was judged by the PI ([name]) to be harmful. Reasons for termination were recorded. 21 patients were terminated or lost to follow-up. Some of these terminations may have been due to hiatuses in the study caused by the untimely death of the principal investigator ([name]) and the untimely occurrence of the COVID pandemic, interfering with patient visits. A list of those terminated or lost to follow-up are reported in Table _____. As a result, an additional 30 patients were accrued above the planned prespecified number, to achieve appropriate statistical power.

There were two co-primary outcome measures: Clinician Global Inventory-Improvement (CGI-I) assessment at week 6 and the change-in-baseline at 6 weeks in International RLS Study Group Severity Scale (IRLS) score. The Patient Global Inventory-Severity (PGI-S) was a secondary outcome measure (PGI-S). The IRLS and PGI-S were obtained at the clinic visits and at each telephone evaluation, while the CGI-i was only obtained at the Week-6 study endpoint.

Statistical analysis

Baseline and follow up laboratory values were described overall and within each study group. Means and standard deviations and medians and ranges were produced for continuous variables, and frequency counts and percentages were generated for describing variables that were dichotomous or

polytomous in nature. Changes in laboratory values from baseline to follow up were calculated and the mean change in values was compared using t-tests.

Results

Baseline lab values of all subjects and by Group are found in Table 1. There was a significant difference between baseline ferritin and TSAT values. Group A had a higher baseline ferritin and TSAT values than Group B.

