Mean (SD)	88.7 (77.3)	82.2 (7.8)	95.4 (110.4)	
Median (IQR)	83 (75.5, 87.0)	83.9 (77.9, 86.3)	81.5 (71.6-87.0)	
Min-Max	56.5, 825.0	58.7, 100.0	56.5, 825.0	

¹ P value comparing Group A vs. Group B using Kruskal-Wallis Test.

Table 2. Follow-up hemoglobin and iron parameters for all subjects and by group.

	Total	Group A	Group B	P-value¹
Hemoglobin	n=70	N=36	N=33	.833
Mean (SD)	14.4 (11.8)	12.5 (1.0)	16.6 (17.0)	
Median (IQR)	12.4 (11.7, 13.3)	12.6 (11.9, 13.2)	12.3 (11.7, 13.4)	
Min-Max	9.7, 105.0	10.4, 14.3	9.7, 105.0	
Ferritin	n=70	N=36	N=33	<0.0001
Mean (SD)	132.8 (136.7)	223.4 (136.6)	37.1 (29.5)	
Median (IQR)	66.5 (27.0, 214.0)	209.5 (127.5, 308.5)	33.0 (21.0-40.0)	
Min-Max	7.0, 620.0	11.0, 620.0	7.0, 159.0	
TSAT	n=70	N=36	N=33	0.026
Mean (SD)	24.4 (13.3)	27.7 (10.0)	21.4 (15.5)	
Median (IQR)	24.0 (14.0, 31.0)	28.0 (20.5, 32.0)	16.0 (12.0-28.0)	
Min-Max	7.0, 89.0	13.0, 59.0	7.0, 89.0	
MCV	n=70	N=36	N=33	0.21
Mean (SD)	95.1 (93.7)	106.4 (130.2)	83.3 (10.6)	
Median (IQR)	86.0 (82.0-88.6)	86.8 (82.7, 88.8)	85.1 (80.0-88.1)	
Min-Max	36.8, 864.0	36.8, 864.0	38.7, 101.0	

¹ P value comparing Group A vs. Group B using Kruskal-Wallis Test.

Table 3. Change in hemoglobin and iron parameters from baseline to follow up for all subjects and by group.

	Total	Group A	Group B	P-value¹
Hemoglobin	N=70	N=36	N=33	0.17
Mean (SD)	3.5 (12.0)	1.2 (1.3)	6.0 (17.2)	
Median (IQR)	1.4 (0.2-2.3)	1.4 (0.2, 1.8)	1.7 (0.3, 3.3)	
Min-Max	-0.9, 95.6	-0.9, 5.0	-0.9, 95.6	
Ferritin	N=67	N=34	N=33	<0.0001
Mean (SD)	113.1 (130.4)	200.3 (133.0)	23.3 (21.2)	
Median (IQR)	35.0 (18, 579)	190.0 (103.0, 290.0)	20.0 (9.0, 27.0)	
Min-Max	-7, 579	-1.0, 579.0	-7.0, 102.0	
TSAT	N=68	N=35	N=33	0.007
Mean (SD)	14.4 (12.6)	16.5 (7.5)	12.2 (16.3)	
Median (IQR)	13.5 (6.5, 19.4)	16.0 (11.0, 20.0)	7.0 (3.0, 18.0)	
Min-Max	-17.0, 82.0	-5.0, 37.7	-17.0, 82.0	
MCV	N=70	N=36	N=33	0.49
Mean (SD)	4.2 (129.9)	24.2 (130.9)	-17.6 (129.5)	
Median (IQR)	3.2 (-0.2, 8.2)	3.3 (-0.4, 7.6)	3.1 (1.2, 9.5)	
Min-Max	-736.9, 784.4	-58.4, 784.4	-736.9, 21.1	

¹ P value comparing Group A vs. Group B using Kruskal-Wallis Test.

Table 4. Change in patient severity scores from baseline to follow up, and follow up patient and clinical global impression scores for all subjects and by group.

	Total	Group A	Group B	P-value¹
Change in patient severity score²	N=57	N=30	N=27	0.24
Mean (SD)	-1.9 (1.8)	-1.7 (1.8)	-2.1 (1.9)	
Median (IQR)	-2.0 (-3.0, -1.0)	-2.0 (-3.0, -1.0)	-3.0 (-4.0, -1.0)	
Min-Max	-5.0, 2.0	-5.0, 2.0	-5.0, 2.0	

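### No stated blinding measure keeps post-dose iron panels from the week-6 CGI rater, and ferritin would reveal the arm of most patients

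*SAP*

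**What the plan says.** **The outcome and its rater.** The protocol (Study Design) makes the CGI-2 at 6 weeks the primary outcome. The SAP (Methods) states: "There were two co-primary outcome measures: Clinician Global Inventory-Improvement (CGI-I) assessment at week 6", the other being the IRLS change. On who rates, the SAP says only that at six weeks "another clinic visit was scheduled so a CGI form could be completed by involved medical personnel".

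**The panels.** The protocol (Blood tests obtained) schedules the iron panel and hemoglobin "at screening prior to treatment and at 4 and 6 weeks after the first treatment". It adds: "The iron panel will include serum iron, ferritin, transferrin saturation and total iron binding capacity". Samples are taken routinely at the site's office, "but in special cases may be arranged through a remote office". The Risk Benefit section treats the blood tests as routine care. In the SAP the week-6 blood is drawn at the same visit as the CGI.

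**The blinding.** Across the protocol (Randomization, Dosing, Blinding) and the SAP (Summary, Methods), the measures are:
- a separate treatment nurse who makes the assignment and treats;
- a coordinator who is absent during treatment and cannot see treatment files;
- double-dummy treatment, with opaque pill bottles and eye masks during infusions;
- a study number for data evaluation that differs from the consent number;
- a general SAP statement that investigators and analysts were blind until the analysis was complete.

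Laboratory results are not mentioned in any of these.

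**The week-6 decision.** Open-label ferumoxytol may be offered to non-responders. The protocol (Subject schedule) says: "This option will be given only if the patient continues to meet all the inclusion/exclusion criteria for the study noted below". Those criteria include ferritin, TSAT and hemoglobin.

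**The concern.** The CGI is a clinician's judgement, so its protection depends on the rater not knowing the arm. The measures above hide the drug and the treatment record. They do not hide the biological effect of IV iron, which is a large rise in ferritin. Week-4 blood is taken about two weeks before the rating, and nothing says that its result is kept from whoever completes the form.

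The direction of any expectation is on record: the protocol's introduction says that IV iron is assumed to be the better choice for these patients. A rater who recognises the arm could, without intending to, score towards that expectation. This would affect the comparison of the arms and also the CGI effect size for each treatment, which is a primary objective of the protocol.

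**Working it through.** **Inputs** (SAP Tables 2 and 3, groups as labelled there)
- Follow-up ferritin, A (n=36): median 209.5, quartiles 127.5 and 308.5, mean 223.4, SD 136.6, range 11 to 620.
- Follow-up ferritin, B (n=33): median 33.0, quartiles 21.0 and 40.0, mean 37.1, SD 29.5, range 7 to 159.
- Change in ferritin: A (n=34) quartiles 103 and 290; B (n=33) range −7 to 102.

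**1. The printed comparison.** Welch t = (223.4 − 37.1)/√(136.6²/36 + 29.5²/33) = 186.3/√(518.3 + 26.4) = 186.3/23.34 = 7.98, p about 1×10⁻⁹. This agrees with the printed Kruskal-Wallis p < 0.0001.

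**2. Identifying the arm without a model.** By the quartiles, at most 9 of 36 in A lie below 127.5 and at most 8 of 33 in B lie above 40. Any cut between 40 and 127.5 is therefore right for at least (69 − 17)/69 = 52/69 = 75%. At the pooled median, 66.5, let a be the A values below and b the B values above. About half of all values must lie below, so a + 33 − b is 34 or 35. Since B's maximum is 159, b ≥ 1 and hence a ≥ 2. At best 66/69 = 96% are right.

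**3. Identifying the arm with a log-normal model.** Log-SD = ln(Q3/Q1)/1.349:
- A: ln(308.5/127.5)/1.349 = 0.655.
- B: ln(40/21)/1.349 = 0.478.
- AUC = Φ(ln(209.5/33)/√(0.655² + 0.478²)) = Φ(1.848/0.811) = 0.989.
- At a cut of 80, 92.9% of A lie above and 96.8% of B below.

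Fitting to means and SDs instead gives AUC 0.982. A plain normal model, a poor fit to skewed data, gives 0.91.

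**4. Whether the model is too kind.** Under the quartile fit, A's minimum is at z = ln(11/209.5)/0.655 = −4.5, about 1 in 290,000. B's maximum is at z = ln(159/33)/0.478 = 3.3, or about 0.016 expected among 33. Both occurred, so the real tails are heavier and 0.98 to 0.99 is optimistic.

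**5. Change from baseline.** A's lower quartile (103) exceeds B's maximum (102). A rise of 103 or more therefore occurs in about 75% of A and in nobody in B.

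**6. Other panel items.** Back-calculating from the printed p-values, AUC = 0.5 + z√((n₁+n₂+1)/(12n₁n₂)):
- follow-up TSAT (p = 0.026): 0.66;
- change in TSAT (p = 0.007): 0.69;
- follow-up hemoglobin (p = .833): 0.51.

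Ferritin is the revealing item.

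**7. Possible consequence (illustration).** Assume no true difference, 65% response, 38 and 34 rated patients (Table 4), 90% of IV patients identified, and a share s of their non-responders upgraded. The observed IV rate is 0.65 + 0.35 × 0.9 × s. Rejection by the protocol's Fisher test (two-sided 0.05 assumed) is:

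| s | observed IV rate | rejection |
|---|---|---|
| 0 | 65% | 3.9% |
| 0.2 | 71.3% | 7.7% |
| 0.3 | 74.5% | 12.7% |
| 0.5 | 80.8% | 30% |

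At s = 0.3, true rates from 50% to 80% give 16.1% down to 6.6%. Only the product of the two shares matters: identifying 75% with s = 0.24 gives 0.18, the same as 0.9 × 0.2, and so 7.7%. The documents give no basis for choosing s.

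**The case against.** The strongest reply is that the documents describe a serious blind and nowhere say that a rater looked at a panel. The SAP states that investigators were blind to assignment. That is correct and must be reported, but the statement gives no procedure for laboratory results.

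Four stronger readings are tempting, and the documents do not support them.

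- *The open-label check makes staff read the panels before rating.* The offer goes to patients already classed as non-responders by the CGI, so eligibility can be checked afterwards. Week-6 blood is drawn at the rating visit, and nothing says the result was back. No text requires anyone to use the week-4 result, although that is the more plausible route.
- *The coordinator reviews post-dose values.* The SAP sentence, "The research coordinator reviewed the responses to the questionnaire, their clinical history and recent blood values to ensure inclusion criteria were met", describes screening before consent. The coordinator is not named as the CGI rater either.
- *The panels reveal the arm almost perfectly.* That fits neither TSAT nor hemoglobin, and for ferritin the ranges overlap.
- *The ratings were biased towards IV iron.* CGI means are 2.1 and 2.1 (p = .80). IRLS change favours Group B (p = 0.047), the apparent oral arm. A reader might take that contrast as a sign of inflated CGI scores in Group A, but the patients' own global impression is also 2.1 and 2.1 (p = .72).

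It is also fair to say that the protocol ranks the comparison between treatments as a tertiary goal. That lowers the stakes for the test, but not for the CGI effect sizes. A null result does not show that the blind held, either.

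**Conclusion.** The point stands as an unprotected risk to a subjective primary outcome, not as a demonstrated bias or a broken blind. Neither document keeps post-dose ferritin from the CGI rater, identifies that rater, or sets the order of rating and result. A rater who saw the value could place at least 75% of patients in the right arm without any distributional assumption, and over 90% under a log-normal model that is somewhat optimistic.

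This rests on three inferences. Group A is taken as the IV arm because its mean ferritin rise is 200.3 against 23.3; the SAP has not decoded the labels. The tables do not say whether follow-up ferritin is the week-4 or the week-6 sample. Access to the panels is inferred from the silence of the blinding text. The rejection rates in the illustration show what could happen under stated assumptions and do not estimate what did.

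**What to change.** **Protocol, for any further rating.** State that the week-6 CGI is completed and signed before any post-baseline iron panel, from week 4 or week 6, is made available to the rater, and that open-label eligibility is checked only after signature. If safety requires review of week-4 results, a person other than the rater does it. The cost is one sentence and an order of forms, with a short delay in the open-label decision.

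**SAP, for data already collected.** An order of forms cannot be imposed afterwards, so the remedy is disclosure:
- State who completed the CGI and whether the week-4 or week-6 panels were available to them.
- If rating and result dates were recorded, add a sensitivity analysis limited to ratings made before results were known. Take the date patient by patient, because a Table 4 footnote says the global scores were assessed at 1 to 6 weeks. If dates were not recorded, say so.
- Interpret the CGI alongside the patient global impression, which Table 4 already reports.

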The study is a randomized, comparative open label study to evaluate effect size and time course of treatment response for RLS-IAD over 6 weeks with a 46-week follow-up extension. Two medications and placebos will be used with equal random assignment to both groups

- Ferumoxytol intravenous (IV) 1020 mg – 2 vials of 510 mg (IV push, 2-3 mins) each given 2-7 days apart
- Ferrous sulfate 325 mg (oral) tabs morning and evening.
- Placebo: oral vitamin C 500 mg tabs, Saline infusion

Primary outcome is the CGI-2 score at 6 weeks after treatment starts. IV ferumoxytol 1020 mg treatment (2 separate doses 510 mg 2-7 days apart) will be offered to those not significantly responding (CGI-2 scores less than much or very much improved) at 6 weeks after oral-iron treatment and still meeting all requirements for entry to study. All responders will be followed for 12 months after treatment.

Study Objectives

Primary objectives

1. Determine relative effect sizes of standard IV and oral iron treatment of RLS with iron deficiency anemia for the PGI-2/CGI-2 (much and very much improved) and for IRLS scores
2. Determine time course of treatment response for IRLS, PGI-1 and PGI-2 scores

Secondary objectives

1. Estimate survival times for effective treatment (no return to other RLS medications) for 1 year after treatment
2. Evaluate possible predictors of treatment response
 - a. Iron status or iron response
 - b. IRLS severity
 - c. Subject characteristics (age, gender)
 - d. Medical factors affecting iron status

Tertiary/exploratory objectives

1. Evaluate significance of efficacy differences if any between oral and IV iron treatments at 6 weeks after treatment: Hierarchical testing first for the percentage with CGI-2 of much or very much improved and second for change from baseline in the IRLS score.
2. Evaluate efficacy benefits of each treatment for usual outcomes related to RLS morbidity: sleep, fatigue, quality of life, and mood.
3. Compare lymphocytes of RLS-IAD and non RLS-IAD for differences in iron related proteins.

Study Procedures

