The percentage responding will be evaluated for each drug condition to determine overall effect size at 6 weeks after treatment. This will be calculated for the IRLS scale and the PGI as change from baseline and for the CGI with response determined as much or very much improved (scores of 1 or 2). All scores greater than 2 on the CGI are considered to indicate no significant response. The onset of treatment will be described as the percentage showing much or very much improvement at each of the evaluations and by the change in IRLS score from baseline at each evaluation. The duration of treatment over the 12 month follow up will be described as the percentage of responders and the IRLS change from baseline at each time point for both oral and IV iron. The oral iron treatment will be stopped for all subjects at the 6-week time point.

The outcomes for the oral versus IV treatments at 6 weeks will be compared using a standard unpaired unequal variance t-test for the change in IRLS scores from baseline. The number of responders compared to no-responders will be compared using the Fisher Exact test.

Sample Size

Uncontrolled experience observing IDA patients with RLS indicated that about 80% responded to IV iron (about 1000mg dose) and 50% responded to standard oral iron treatment over 6 to 12 weeks. These percentage outcomes require a sample size of 70 (35 with each treatment) to provide a power of >80% with alpha = 0.05 to test for differences between these treatments. This was considered a reasonable sample to ascertain the effect size of the two treatments and to provide enough positive outcomes to evaluate time course for improvement with treatment and persistence of the treatment effect.

Breaking the blind

The randomization is in cohort blocks of 10, 5 with each treatment. The blind for the form of initial treatment will be broken for every cohort of 10 treated patients after all members of a cohort have completed the study. The blind may also be broken for specific subjects if the treatment information is needed for medical care of the patient.

Concomitant Medication

Permitted Medications

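### The SAP calls CGI-I and IRLS change co-primary with no decision rule, departs from the Protocol's exploratory order (CGI-2 responders first, IRLS second), and reports neither of the Protocol's two tests

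*SAP*

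**What the plan says.** **Protocol.** Study Design names one primary outcome: "Primary outcome is the CGI-2 score at 6 weeks after treatment starts". For the between-arm comparison, the Tertiary/exploratory objectives fix an order: "Hierarchical testing first for the percentage with CGI-2 of much or very much improved and second for change from baseline in the IRLS score". Statistical Analyses assigns the tests. IRLS change gets an unpaired unequal-variance t-test, and for response, "The number of responders compared to no-responders will be compared using the Fisher Exact test". The Rationale ranks treatment differences as a tertiary goal.

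For estimation the Protocol is wider. Primary objective 1 seeks effect sizes "for the PGI-2/CGI-2 (much and very much improved) and for IRLS scores". The section on RLS clinical evaluations begins "The primary clinical evaluations will be the clinician global rating of improvement (CGI-2), patient global rating of RLS severity (PGI-1") and adds the IRLS.

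**SAP.** The Methods paragraph on outcome measures says "There were two co-primary outcome measures: Clinician Global Inventory-Improvement (CGI-I) assessment at week 6 and the change-in-baseline at 6 weeks" in IRLS, and makes PGI-S secondary. It states no testing order, significance level or success rule. The SAP Summary instead describes the patient and clinical global impression scores as the primary outcomes, and says 30 patients were added to keep the prespecified analysis. The Statistical analysis section names a test only for laboratory values. Table 4 gives the CGI score with Kruskal-Wallis p=.80 and no responder counts. Table 6 gives IRLS change with Kruskal-Wallis p=0.047.

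**The concern.** Co-primary can mean that both outcomes must succeed, or that either may. The two readings have different error rates, and here they give different answers. IRLS change is the only clinical efficacy comparison in Tables 4 to 6 below 0.05, so the missing rule decides how that result may be described.

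The Protocol had settled this. Under its order the IRLS p-value is nominal unless the CGI responder test passes. The SAP omits the order without explanation, does not report the first test, and uses a different test for the second. Its text already contains results, so a rule chosen now would be chosen with the p-values in view.

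**Working it through.** **1. The plan's own figure.** Sample Size (Protocol) gives 35 per arm for 80% versus 50% responding, alpha 0.05. With unpooled variances, two-sided, 80% power:

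n = [0.8×0.2 + 0.5×0.5] × (1.960 + 0.842)² / 0.30² = 0.41 × 7.849 / 0.09 = 35.8, so 36 per arm or 72 in total.

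This is within two patients of 70. The trial was sized on the proportion responding, not on IRLS.

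**2. Tabled p-values under each possible rule** (CGI .80, Table 4; IRLS 0.047, Table 6).

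| Rule | Check | IRLS counts? |
|---|---|---|
| Both must succeed at 0.05 | .80 > 0.05 | No |
| Bonferroni | 2 × 0.047 = 0.094 > 0.05 | No |
| Holm | smaller p: 0.047 > 0.025 | No |
| Hochberg | .80 > 0.05, then 0.047 > 0.025 | No |
| Either, unadjusted | 0.047 < 0.05 | Yes |

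Family-wise error of the last rule is 1 − 0.95² = 0.0975 for independent tests, and about 0.091 at an assumed correlation of 0.5.

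**3. The Protocol's IRLS test, from Table 6.** Group A: mean -8, SD 7.7, n=37. Group B: mean -12.2, SD 9.5, n=36.

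- SE = √(7.7²/37 + 9.5²/36) = √(1.602 + 2.507) = 2.03
- t = 4.2 / 2.03 = 2.07, df 67.3, p = 0.042; difference 4.2 points, 95% CI 0.15 to 8.25

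This takes Group A's mean as -8.0, but it is printed without a decimal. If it was rounded to a whole number (-8.5 to -7.5), and the other entries vary within their rounding, p runs from 0.021 to 0.078. The Total mean of -10.1, applied to 37 + 36 patients, confines Group A to -8.20 to -7.91 and p to 0.035 to 0.057. The Protocol's own test may therefore not be below 0.05. The low end of 0.021 would meet Holm's 0.025, but the Total mean excludes it.

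**4. What Table 4 implies for the Fisher test.** I enumerated whole-number CGI scores matching the printed n, range, mean, SD, median and quartiles: A n=38, median 2; B n=34, median 1.5; Total n=72, median 2.0. Responders are scores 1 and 2.

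The Total column matters. Nineteen responders in A with median 2 requires nineteen scores of 1, and median 1.5 in B requires seventeen. Pooled, that is 36 ones among 72 and a median of 1.5, not the printed 2.0, so those cases drop out.

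| | Quartiles exactly 1 and 3 | Quartile of 2.5 may print as 3 |
|---|---|---|
| Smallest Fisher p, Total column imposed | 0.087 (28/38 v 18/34) | 0.049 (29/38 v 18/34) |
| Also with tie-corrected Kruskal-Wallis p=.80 | 0.14 (28/38 v 19/34) | 0.083 (29/38 v 19/34) |

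**5. Timing and counts.** Table 4 footnote 3 places the CGI scores at weeks 1 to 6. Table 6 footnote 2 lists 2 + 4 + 5 + 61 = 72 follow-ups, 11 of them before week 6. The arms sum to 37 + 36 = 73, and the Total is 74.

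**The case against.** **IRLS was always among the primary measures.** This is correct for estimation, as primary objective 1 and the list of primary evaluations show. A reader might infer that IRLS was promoted after a favourable result. The documents do not support that: the outcome is not new, and nothing shows when the co-primary wording was written. What is missing is the testing rule.

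**This is a pilot with exploratory testing, and the SAP claims no success.** Both parts stand. SAP Results says only that Group B had the larger IRLS reduction, reports no CGI difference, and carries an analyst's comment that results still need checking. That limits the severity. The label co-primary still implies more than the Protocol allows.

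**The IRLS result is nominal because no Fisher test is reported.** A reader might infer this, but it does not follow: an unreported first test leaves its outcome unknown. The firmer ground is that between-arm testing is tertiary and exploratory under the Protocol.

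**The first test failed.** This too goes further than the documents. The tabled scores make it likely, but they may include values from before week 6.

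**The SAP's week-6-only CGI is simply wrong.** The Protocol says of the primary evaluations "These will be obtained at each clinic visit and at each telephone evaluation, except CGI-2 will only be obtained after the treatment", and Table 4 footnote 3 agrees with it. But SAP Methods separately says the six-week visit was arranged so that the CGI form could be completed. The Protocol sentence "The onset of treatment will be described as the percentage showing much or very much improvement at each of the evaluations" does not name the CGI, and primary objective 2 defines time course by IRLS, PGI-1 and PGI-2. The passages conflict, and no single one is clearly the error.

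**Conclusion.** The point holds and should be fixed, although it invalidates no claim the SAP currently makes. The SAP labels two outcomes co-primary without a rule, contradicts its own Summary on which outcomes are primary, and reports neither test the Protocol assigned to the between-arm comparison.

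The IRLS p-value of 0.047 is exploratory on any reading. Under the Protocol's order it is also nominal unless the CGI responder test passes, and that result is not reported. On the tabled p-values, only an unadjusted either-wins rule would let it count.

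This rests on four assumptions: CGI-2 and CGI-I are the same instrument; the summary statistics are printed correctly; Table 6 covers 37 and 36 patients; and, where p=.80 was imposed, it was tie-corrected. On the tabled scores the first test appears not to have passed, but the 0.087 and 0.14 figures (0.049 and 0.083 on the looser quartile reading) are not bounds on a Fisher test of week-6 data. The SAP does not say which arm is Group B, so the direction of the IRLS difference cannot be read as favouring IV or oral iron.

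**What to change.** In the SAP outcome-measures paragraph, replace the co-primary sentence with wording such as:

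> The between-arm comparison is exploratory. The first test is the proportion much or very much improved on CGI-2 (CGI-I) at 6 weeks, by two-sided Fisher exact test at 0.05. Change in IRLS from baseline to 6 weeks is tested second, by two-sided unequal-variance t-test; its p-value is nominal unless the first test passes.

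Then:

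- Make the SAP Summary name the same primary outcome.
- Add responder counts per arm and the Fisher p to Table 4. Add the t-test p and the IRLS difference with its 95% CI to Table 6.
- State, with a date, that the order and the tests restore the Protocol. State also that two-sidedness, the 0.05 level for the hierarchy (the Protocol gives 0.05 only under Sample Size) and the confidence intervals are additions written with results present.
- If co-primary is kept, state the rule (both must succeed, or Holm), justify the departure, and make the same disclosure.

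Secondary items: reconcile the statements on when CGI was obtained; show CGI and IRLS for observed week-6 values as well as under the most-recent-value note below Table 4; reconcile the Table 6 counts of 74, 73 and 72.

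The cost is two wording changes, one dated disclosure, and two tests on existing data, each run on two data versions. The downside for the authors is that, on the tabled data, IRLS change cannot be presented as a significant primary result.
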